5.4. Subject Withdrawal

5.4.1. Reasons for Withdrawal

Dentists are free to withdraw from participation in the study at any time upon request.

5.4.2. Handling of Practitioner and Patient Withdrawals

Dentists who withdraw from the study will not be replaced. **5.5. Premature Termination** or Suspension of Study

This study may be suspended or prematurely terminated if there is sufficient reasonable cause. Written notification, documenting the reason for study suspension or termination, will be provided by the suspending or terminating party. If the study is prematurely terminated or suspended, the SPI will promptly inform the Institutional Review Board (IRB) and will provide the reason(s) for suspension or termination. Circumstances that may warrant termination include, but are not limited to:

- Insufficient adherence to protocol requirements.
- Data that is not sufficiently complete and/or evaluable.
- Determination of unexpected, significant, or unacceptable risk to study participants.
- Determination of futility.

6. STUDY SCHEDULE

6.1. Stage 1 - Survey Component: Enrollment/Baseline

- Eligible dentists will be identified from responses to National Dental PBRN Enrollment Questionnaire by Westat and will be randomly selected for participation based on inclusion/exclusion criteria; Westat will deliver contact information and selected Enrollment Questionnaire data to the SPI.
- Dentists will be invited to complete an online survey in 3 waves of increasing size to adjust for a balanced regional representation.
- Completion of the survey will indicate that practitioners have read informed consent information and will imply consent. A waiver of signed consent will be sought from the IRB.

6.2. Stage 2 - Retest of the Survey (See Section 7.2)

- Dentists randomly selected from among those participants who have completed the survey within the first two weeks of their survey launch wave will be sent a second online survey request by email approximately two weeks after the receipt of their first completed survey.
- Dentists will be informed that they have approximately one week to respond to the invitation for retest. If a selected retest participant has not completed their retest within this approximate one-week timeframe, the link to the retest survey will be disabled and a new potential retest participant will be selected from those having already completed the survey until a total of approximately 50 retests have been completed.
- Completion of the retest survey will indicate tacit consent.

6.3. Stage - 3 Merging Practitioner Survey with Enrollment Questionnaire

- Survey and Network enrollment data will be linked using participant IDs.
- Contact information will be removed from the final merged dataset and data will be stored/saved using Unique Participant IDs.

7. STUDY PROCEDURES/EVALUATIONS

7.1. Practitioner Survey Development

The initial draft of this survey instrument was developed with feedback from the initial study team (including clinical providers, dental researchers and survey experts) and underwent a cognitive "think aloud" process. We asked several (N=11) dentists to read the questions aloud and verbally express what they thought the question was addressing and how they reasoned through the response options. Additionally, we created two versions of the items - one sorted by hypothesis (i.e., content) and one sorted by cognitive demand and content. The latter form provided us the opportunity to see if we could reduce the cognitive demand of the total survey by arranging the items with respect to the way a respondent needed to think about a question. Historical questions, for example, were grouped together within a content area to ensure that once a respondent began thinking about what happened in the past, the effort to recall these past events could be reused (in effect) instead of immediately discarding the recalled events from working memory. This iterative development process has maximized dental practitioner input in an effort to increase the relevance of the survey and its findings to dentists. The finalized survey instrument was then piloted in its current online format using the REDCap electronic data capture tool for data collection and management.

7.2. Survey Testing-Retesting

The online version of the survey will be administered twice to a subset of approximately 50 dentists to assess the test-retest reliability of the survey. Dentists who complete the online version of the initial survey will be sent a second online survey request by email approximately two weeks after receipt of the first completed survey.

Retest participants will be randomly selected from among those participants who have completed the survey within the first two weeks of their survey launch wave. Dentists completing their initial survey participation will be entered into a randomizer application (randomizer.org). Once randomly ordered, the first listed ~25 dentists will be selected for invitation to the retest. Each dentist will be given approximately one week to complete the retest. If the retest is not completed within the timeframe, the link to the retest survey will be disabled and the next dentist on the randomized list will be contacted. This process will be continued until 50 dentists complete the retest.

7.3. Website and Survey Pilot Testing

The SPI and Study team will perform extensive internal testing of the REDCap survey, including internet browser compatibility. Study team members will also externally test the website prior to administration with study participants.

7.4. Survey Content

Topical areas addressed in the survey are detailed in Section 3. Some information will be collected from Westat and the National Dental PBRN Enrollment Questionnaire (e.g., demographics and practice characteristics) and will be linked to participants' responses to the study survey.

Survey Administration:

An initial study invitation will be sent to eligible dentists via email. The invitation will include information regarding the study and will contain a unique participation link to the survey embedded in REDCap. Dentists will be informed that the survey would ideally be completed in one sitting and that it will take approximately 20 minutes to complete. However, should participants need multiple sittings to complete the survey, they will be able to do this using the "Save & Return Later" feature within the REDCap survey. Should participants decide to "Save & Return Later," they will be able to return to the REDCap survey with their initial login information. Dentists reaccess the survey using the unique survey link and will need to enter their login information to verify their identity and gain re-entry to their survey. Should dentists not be able to login, they will need to contact the SPI or their RC to receive new login instructions (possibly restart the survey instead of returning to the saved stage). Dentists will receive three email reminders to complete the survey. Those who do not respond to email invitations will be contacted by the RCs regarding their interest in study participation.

Dentists will be encouraged to visit the secure web site to complete the survey. If no feedback is received or the dentist does not complete the electronic survey after multiple follow up attempts over a period of approximately 10 weeks post-invitation, it will be assumed the dentist is not interested in the study. (See Schematic of Study Design).

8. ASSESSMENT OF SAFETY

8.1. Specification of Safety Parameters

Safety monitoring for this study will focus on unanticipated problems (UP) involving risks to participants, including unanticipated problems that meet the definition of a serious adverse event (SAE).

8.1.2. Unanticipated Problems

The Office for Human Research Protections (OHRP) considers UPs involving risks to patients or others to include, in general, any incident, experience, or outcome that meets **all** of the following criteria:

- Unexpected in terms of nature, severity, or frequency given (a) the research procedures that are described in the protocol-related documents, such as the IRB-approved research protocol and informed consent document; and (b) the characteristics of the patient population being studied;
- Related or possibly related to participation in the research (possibly related means there is a reasonable possibility that the incident, experience, or outcome may have been caused by the procedures involved in the research); and
- Suggests that the research places patients or others at a greater risk of harm (including physical, psychological, economic, or social harm) than was previously known or recognized.

8.2. Reporting Procedures

Incidents or events that meet the OHRP criteria for UPs require the creation and completion of an UP report form. OHRP recommends that investigators include the following information when reporting an adverse event (AE), or any other incident, experience, or outcome as an UP to the IRB:

- Appropriate identifying information for the research protocol, such as the title, investigator's name, and the IRB project number;
- A detailed description of the AE, incident, experience, or outcome;
- An explanation of the basis for determining that the AE, incident, experience, or outcome represents an UP;
- A description of any changes to the protocol or other corrective actions that have been taken or are proposed in response to the UP.

To satisfy the requirement for prompt reporting, UPs will be reported using the following timeline:

- UPs will be reported to the IRB and to NIDCR within 2 weeks of the SPI becoming aware of the problem.
- All UPs should be reported to appropriate institutional officials (as required by an institution's written reporting procedures), the supporting agency head (or designee), and OHRP within one month of the IRB's receipt of the report of the problem from the SPI.

All UPs will be reported to NIDCR's centralized reporting system via Rho Product Safety:

- Product Safety Fax Line (US): [name]
- Product Safety Fax Line (International): [contact]
- Product Safety Email: rho [contact]

General questions about SAE reporting can be directed to the Rho Product Safety Help Line (available 8:00AM – 5:00PM Eastern Time):

- US: [name]
- International: [contact]

9. STUDY OVERSIGHT

The GPI and SPI will be responsible for study oversight, including monitoring safety, ensuring that the study is conducted according to the protocol and ensuring data integrity. The SPI will review the survey data for safety concerns and data trends at regular (weekly) intervals, and will promptly report to the IRB and NIDCR any UP, protocol deviation, or any other significant event that arises during the conduct of the study.

10. CLINICAL SITE MONITORING

Clinical site monitoring will not occur for this survey study. The SPI is responsible for launching the survey and collecting data received as part of the survey. The SPI will ensure that the quality and integrity of study data and data collection are maintained. The RCs will be responsible for following up with eligible dentists who are considered non-respondents (see *Section 5.3*) to encourage study participation.

NIDCR reserves the right to conduct independent audits as necessary.

11. STATISTICAL CONSIDERATIONS

11.1. Study Hypotheses

The primary objective of this study is to explore dentists' beliefs and behaviors related to AP guidelines and prescribing practices to prevent distant site infection. The secondary objectives of this study are to explore: Factors related to dentists' adherence to AP guidelines for the prevention of IE and PJI and their influence upon AP prescribing practices; dentists' knowledge about risks for bacteremia and the utility of AP in preventing distant site infection.

11.2. Sample Size Considerations

All objectives of the current study are either descriptive or exploratory - rather than hypothesis testing - in nature. Therefore, standard sample size calculations based on anticipated effect sizes do not apply. However, based on a survey quideline report by Brinkman W-P et al.*, our proposed sample size will allow us to perform statistical analyses for observed small to medium effect sizes (comparing general dentists to specialists, all categories included) and for medium to large effect sizes (specialist subcategories). Our sample size was selected based on the total number of dentists available as of January 7th 2017 (N=4002 including 3002 general dentists (GDs) and 992 specialists, excluding the category "other", see Table 1 below). Our 3-pronged recruitment approach will ensure comparable representation of both general and specialist dentists from all National Dental PBRN regions and minimize the margin of error to compare generalists with specialists overall or to compare some of the specialist subcategories (e.g. pediatric dentists vs. non-pediatric specialists). Table 1 below presents National Dental PBRN enrollment data for each region from Jan 7, 2017. Table 2 presents the number of invited participants and anticipated number of completing participants, per each dentist or region category with respective survey margins of error (MOE) at 95% confidence level. Proposed sample size allows for a margin of error of 3.15% (+/- 0.34 (SD)) on average per region (generalists and specialists combined),

0.05% for general dentists and 2.55% for specialists (all regions combined), at 95% confidence level. The online tool (https://www.qualityoutcomes.com/samplesize.aspx) was used to determine whether samples size per region or per specialty were appropriate to allow for minimal MOE possible.

* Preliminary version of: Brinkman, W-P (2009). Design of a Questionnaire Instrument, Handbook of Mobile Technology Research Methods, ISBN 978-1-60692-767-0, pp. 31-57, Nova Publisher.

Table 1. National PBRN Enrollment as of Jan 7th 2017

					Specialists subcategories							
Region	Dentists	Total Dentists	GDs	SPs	Total SPs	Endo-	Pediatric	Perio-	Prostho-	Oral/Maxillo-	Ortho-	
	all PBRN	w/o "Other"			w/o Other	dontist	Dentist	dontist	dontist	facial Surgeon	dontist	
1. Western	599	583	415	184	168	22	21	11	6	7	101	
2. Midwest	494	481	350	144	131	19	23	17	12	8	52	
Southwest	797	783	594	203	189	27	36	43	11	19	53	
4. South Central	755	744	606	149	138	21	28	27	14	12	36	
5. South Atlantic	585	577	446	139	131	20	20	19	18	4	50	
6. North East	852	834	599	253	235	24	42	37	20	18	94	
Total	4082	4002	3010	1072	992	133	170	154	81	68	386	

 Table 2. Sample size determinations per region and per specialty category (60%) response rate),

 95% confidence level

			Specialists subcategories							
			Total Size	MOE	Endo-	Pediatric	Perio-	Prostho-	Oral/Maxillo-	Ortho-
Region	GDs	Sps	Region	Region	dontist	Dentist	dontist	dontist	facial Surgeon	dontist
1. Western	249	100	350	3.33	13	13	7	4	4	60
2. Midwest	210	79	289	3.65	12	14	10	7	5	31
Southwest	356	113	469	2.87	16	21	26	7	11	32
4. South Central	363	83	446	2.94	13	17	16	8	7	22
5. South Atlantic	268	79	346	3.34	12	12	11	11	3	30
6. North East	359	141	500	2.78	14	25	22	12	11	56
Total Size Cat.	1805	595	2400	1.27	80	102	92	49	41	231
MOE Cat.	0.05	2.55	1.27	-	7.00	6.20	6.59	9.00	10.00	4.10

Final Analysis Plan

Two forms of missing data will be addressed by our analysis of main outcomes. First, we anticipate some degree (approximately 40%) of *total non-response*: dentists sent a unique survey participation link who do not respond/initiate the survey within the study period for a variety of reasons including refusal, non-contact, illness, death, or some other barrier preventing participation. Data missing due to total non-response will be addressed by the following approach: (1) We will describe characteristics of dentists who did not respond to the survey using data from their National Dental PBRN Enrollment Questionnaire; (2) We will then examine and report potential demographic (age, gender, ethnicity) and practice (specialty, practice location, primary practice setting) characteristic differences between respondents and total non-respondents; (3) If significant demographic differences emerge between respondents and non-respondents, sample-

weighting adjustments will be applied to the data; and (4) Main outcomes will be analyzed using both non-weighted and weighted datasets.

Second, we anticipate missing data due to *item non-response*: dentists participating in the survey who fail to provide acceptable responses to one or more of the survey items. Item non-response may occur as a result of a participant refusing to answer a specific item on grounds that it is too sensitive, he/she does not know the answer to the item, or he/she overlooks the item by accident. Items skipped due to planned skip-logic will not be coded as missing data. In instances where the non-response rate for an item is low (<5% of respondent sample missing for given item), pairwise deletion will be applied given that the amount of potential bias in univariate and bivariate analyses for that item will be small.³⁸ Also, in instances where the non-response rate for an item is non-negligible but the missing data is deemed missing completely at random (MCAR), pairwise deletion will be applied. However, in instances of non-negligible item non-response where the MCAR assumption is not valid and data are missing at random (MAR), multiple imputation procedures will be considered.

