SAESerious Adverse Event/Serious Adverse ExperienceSMSSurvey Management SystemSPIStudy Principal InvestigatorUABUniversity of Alabama at Birmingham	RAS	Regional Administrative Site
SMSSurvey Management SystemSPIStudy Principal InvestigatorUABUniversity of Alabama at Birmingham	RC	Regional Coordinator
SPIStudy Principal InvestigatorUABUniversity of Alabama at Birmingham	SAE	Serious Adverse Event/Serious Adverse Experience
UAB University of Alabama at Birmingham	SMS	Survey Management System
	SPI	Study Principal Investigator
UP Unanticipated Problems		
	UP	Unanticipated Problems

PROTOCOL SUMMARY

Title:	Prophylactic Use of Antibiotics in Dental Practice
Précis:	Since the advent of antibiotics in the mid-1940s, and in particular with the first formal recommendations for antibiotic prophylaxis (AP) by the American Heart Association (AHA) in 1955, there has been a significant proliferation of the use of secondary AP in dental practice. ¹⁻³ However, there is increasing controversy about the widespread use of antibiotics for some prophylactic, as well as therapeutic dental purposes, primarily due to concerns about antibiotic resistant bacteria and adverse drug reactions, weak evidence to support the practice of AP, and the costs and inconvenience associated with the use of AP. Consequently, this study aims to identify critical conceptual and standardization gaps in the practice and implementation of AP for patient populations felt to be at increased risk to develop infective endocarditis (IE) and/or prosthetic joint infections (PJI) prior to dental procedures. By surveying approximately 2,500 members of the National Dental Practice-Based Research Network, we expect to reveal some of the common tendencies and practices regarding AP by practitioners across the United States.
Objectives:	The primary objective of this study is to explore dentists' beliefs and behaviors related to antibiotic prophylaxis (AP) guidelines and prescribing practices to prevent local or distant site infection after dental treatment.
	The secondary objectives of this study are to explore: Factors related to dentists' adherence to AP guidelines for the prevention of IE and PJI and their influence upon AP prescribing practices; dentists' knowledge about risks of bacteremia and the utility of using AP to prevent distant site infection.

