4. STUDY DESIGN

This survey questionnaire is a cross-sectional study that is limited to National Dental PBRN dentists who are currently practicing. Approximately 4,000 dentists will be invited to participate (approximately 2,400 respondents expected for an anticipated 60% average response rate, or approximately 2,500 maximum should the response rate be higher). All Network members, at the limited or full participation level, who are general dentists or specialists (N~992) in Endodontics, Periodontics, Prosthodontics, Orthodontics, Pediatric Dentistry, Dental Public Health, Orthodontics, and Oral/Maxillofacial Surgery will be invited to participate. Oral Pathologists and Oral Radiologists will **not** be invited to participate, as they are rarely involved with issues regarding AP.

Based on previous survey research within the Network, we anticipate an approximately 60% completion rate on average. Westat Coordinating Center will be responsible for randomly selecting dentists from within each Network region. Network regional quotas will help to ensure that each region has adequate representation within the survey.

Participation involves the completion of the practitioner AP Prescribing Practices survey. Dentists will complete the survey online through the REDCap survey management system, or upon special request a paper version can be mailed by a study team member at the Coordinating Center to the individual through standard United States Postal Service (USPS), and returned to sender upon completion via a pre-stamped, "no postage necessary" envelope that will accompany the hard copy. The return envelopes will be pre-addressed to the attention of [name] (SPI), and data entry will be performed by one of the designated study team members at the Coordinating Center. The paper, or hard, copy of the survey will be identical to the web-based survey. Westat Coordinating Center will be responsible for providing the SPI with contact information (including active email addresses) for member dentists randomly selected for participation based on inclusion/exclusion criteria. Dentists will be invited via email. The AP Prescribing Practices survey data will be collected via an online survey instrument housed in the Carolinas Medical Center (CMC) REDCap survey management system (SMS).

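### The margins of error in Section 11.2 and Table 2 rest on an undisclosed finite population correction, valid only for network members under random non-response, and the 0.05% for general dentists is wrong either way

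*Protocol*

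**What the plan says.** Section 11.2 takes its population from network enrolment: "N=4002 including 3002 general dentists (GDs) and 992 specialists, excluding the category 'other". The general-dentist count in Table 1 is 3,010, not 3,002. Table 2 gives the expected number of respondents per region and specialty at a 60% response rate, "with respective survey margins of error (MOE) at 95% confidence level". The text summarises these: "Proposed sample size allows for a margin of error of 3.15% (+/- 0.34 (SD)) on average per region (generalists and specialists combined"), then 0.05% for general dentists and 2.55% for specialists. An online calculator is cited, but no formula, assumed proportion or finite population correction is given.

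Section 4 describes the recruitment: "Approximately 4,000 dentists will be invited to participate (approximately 2,400 respondents expected for an anticipated 60% average response rate"). Sections 4 and 6.1 also speak of random selection of dentists, and Section 5.3 of invitation waves adjusted with a random generator. The Final Analysis Plan anticipates "some degree (approximately 40%) of" total non-response, through refusal, non-contact, illness and similar causes. It plans a comparison of respondents with non-respondents, with weighting if demographic differences appear. The Précis in the Protocol Summary expects to reveal some of the "common tendencies and practices regarding AP by practitioners across the United States".

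**The concern.** A finite population correction narrows a margin of error because the sample covers a large share of a fixed population. It is justified when the target is exactly that population and the unobserved part is missing at random. Here the respondents are 60% of the network, so the correction is large. The unobserved 40% are almost entirely people who were invited and did not answer, and the Précis points to a population beyond the network.

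The margins are the protocol's main quantitative statement of precision, and Section 11.2 relies on them to support comparing generalists with specialists and specialist groups with one another. A reader who does not know that the correction is there will take the figures as ordinary sampling margins and overrate what the survey can show about dentists outside the network. The 0.05% would suggest near-perfect knowledge of general dentists, who make up three quarters of the expected respondents.

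**Working it through.** **Inputs.** N per cell from Table 1 (columns without the category of other specialists). n per cell from Table 2. z = 1.96 for 95% confidence. The proportion is not stated. I assume p = 0.5, which reproduces the table. The ratio between corrected and uncorrected margins does not depend on p.

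**Formulas.** Uncorrected margin = 1.96 × sqrt(0.25/n). Correction factor = sqrt((N − n)/(N − 1)). Corrected margin = their product.

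**Example, overall.** 1.96 × sqrt(0.25/2400) = 2.00%. Factor = sqrt(1602/4001) = 0.633. Product = 1.27%, as stated.

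| Cell | N | n | Uncorrected % | Corrected % | Stated % |
|---|---|---|---|---|---|
| Western | 583 | 350 | 5.24 | 3.31 | 3.33 |
| Midwest | 481 | 289 | 5.76 | 3.65 | 3.65 |
| Southwest | 783 | 469 | 4.53 | 2.87 | 2.87 |
| South Central | 744 | 446 | 4.64 | 2.94 | 2.94 |
| South Atlantic | 577 | 346 | 5.27 | 3.34 | 3.34 |
| North East | 834 | 500 | 4.38 | 2.78 | 2.78 |
| Regional mean | | | 4.97 | 3.15 | 3.15 |
| All | 4002 | 2400 | 2.00 | 1.27 | 1.27 |
| Specialists | 992 | 595 | 4.02 | 2.54 | 2.55 |
| Endodontists | 133 | 80 | 10.96 | 6.94 | 7.00 |
| Pediatric dentists | 170 | 102 | 9.70 | 6.16 | 6.20 |
| Periodontists | 154 | 92 | 10.22 | 6.50 | 6.59 |
| Prosthodontists | 81 | 49 | 14.00 | 8.85 | 9.00 |
| Oral surgeons | 68 | 41 | 15.3 | 9.72 | 10.00 |
| Orthodontists | 386 | 231 | 6.45 | 4.09 | 4.10 |
| General dentists | 3010 | 1805 | 2.31 | 1.46 | **0.05** |

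The corrected formula also gives the stated regional SD of 0.34. The regions agree within 0.02 and the subcategories within about 0.3. No stated figure matches the uncorrected formula. The factor is 0.63 to 0.64 throughout, so the uncorrected margins are about 1/0.633 = 1.58 times as wide.

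**General dentists.** Using N = 3,002 from the text instead of 3,010 still gives 1.46%. To reach 0.05% with the correction, (3010 − n)/n must equal 3009 × (0.0005/0.98)² = 0.00078, so n is about 3,008 of 3,010, against the 1,805 in Table 2.

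**Effect on a comparison that Section 11.2 names.** The margin for the difference between generalists and specialists is sqrt(1.46² + 2.54²) = 2.9 points with the correction and sqrt(2.31² + 4.02²) = 4.6 points without.

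**When the corrected figure is right.** In a simulation, all 4,002 were invited and 60% answered completely at random. 1.96 times the SD of the estimate around the network's true value was 1.26 points, in agreement with 1.27.

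**Non-response bias.** Bias = 0.4 × (respondent minus non-respondent prevalence). A gap of 1.27/0.4 = 3.2 points gives a bias equal to the whole stated overall margin. The size of the gap is unknown. Over an assumed range of 5 to 10 points, the bias is 2 to 4 points, which equals or exceeds even the uncorrected 2.00%.

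**The case against.** The strongest reply is that the correction is legitimate for the study's own population. Section 4 limits the study to network dentists, Section 11.2 names 4,002 as the total, and the objectives in Section 3 claim no national estimate. If non-response is random, the corrected margins are right for that population, as the simulation shows. A margin of error conventionally covers sampling error only, and the Final Analysis Plan already addresses non-response through comparison and weighting. The objectives are descriptive or exploratory, and the sample size was set by the dentists available. All of this stands. It leaves the correction undisclosed, its two conditions unstated in Section 11.2, the Précis pointing beyond the network, and the 0.05% unexplained.

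Three stronger readings are tempting, and the protocol does not support them.

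- A reader might infer that non-response itself makes the margins about 37% too narrow (1 − 0.63). It does not. Random non-response leaves the corrected margin valid for the network. Otherwise the problem is bias, which dropping the correction neither measures nor repairs.
- A reader might infer that final confidence intervals will be too narrow and will yield false regional or specialty differences. Nothing in the protocol says that the analysis will apply the correction.
- A reader might take the random-selection wording in Sections 4 and 6.1 as justifying the correction, or ignore it and say flatly that everyone is invited. The wording is inconsistent with inviting all eligible members. With about 4,000 invited out of 4,002, though, random selection leaves out almost nobody, so the shortfall to 2,400 is still non-response.

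**Conclusion.** The point holds in two parts. First, every stated margin but one depends on an unstated correction of about 0.63 and is valid only for network members with random non-response. For practitioners across the country the correction does not apply. On the optimistic assumption that responders are a random sample of that population, the margins are about 1.58 times the stated ones: overall 2.00% against 1.27%, regional mean 4.97% against 3.15%, specialists 4.02% against 2.55%, and subcategories 6.45 to 15.3% against 4.1 to 10.0%. Network members are not a probability sample of US dentists, so even these wider margins are conditional.

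Second, the 0.05% for general dentists is a separate error that the correction does not explain. The value is 1.46% with it and 2.31% without. The absolute figures assume p = 0.5; the factor of 1.58 does not.

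**What to change.** In Section 11.2 and Table 2:

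1. Replace the 0.05% for general dentists, in the text and in the table, with 1.46% (corrected) and 2.31% (uncorrected). Reconcile 3,002 with 3,010.
2. Show the uncorrected margins beside the corrected ones, and label the corrected column 'network members only, assuming non-response is random'. State the formula and the assumed proportion.
3. State that neither column covers non-response bias, that this bias equals 0.4 × (respondent minus non-respondent prevalence), that it is addressed only through the weighted analysis in the Final Analysis Plan, and that dropping the correction does not repair it.

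The cost is restated and less favourable precision figures. The sample and the conduct of the survey do not change.

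### The 0.05% margin of error stated for 1,805 general dentists is wrong; by the method that reproduces the rest of Table 2 it is 1.46%

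*Protocol*

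**What the plan says.** Protocol section 11.2 introduces Table 2 as giving invited and expected participants "with respective survey margins of error (MOE) at 95% confidence level". Three margins are then stated in the text:

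- Regions: "Proposed sample size allows for a margin of error of 3.15% (+/- 0.34 (SD)) on average per region".
- General dentists and specialists: "0.05% for general dentists and 2.55% for specialists (all regions combined), at 95% confidence level".

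The last rows of Table 2 repeat the category figures. The expected respondents read "Total Size Cat. 1805 595 2400" (general dentists, specialists, all), and the margins beneath them read "MOE Cat. 0.05 2.55 1.27". The table is built on a 60% response rate.

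The populations come from Table 1, whose total row reads "Total 4082 4002 3010 1072 992". In order, these are all dentists, all without the category 'other', general dentists, all specialists, and specialists without 'other'. The text of section 11.2 gives a different general-dentist count: "N=4002 including 3002 general dentists (GDs) and 992 specialists".

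**The concern.** A margin of 0.05% would mean that estimates for general dentists carry almost no sampling error. General dentists are 1,805 of the 2,400 expected respondents, or 75%, so this is the stated precision for most of the sample. The figure is far out of line with its neighbours: the whole sample, which contains these dentists, is given 1.27%, and the 595 specialists 2.55%. It appears in both text and table, so it is not a fault of text extraction. Section 11.2 also names the comparison of generalists with specialists as one that the sample is meant to serve, and the generalist margin feeds into that comparison.

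**Working it through.** **Inputs.** Expected respondents n are from Table 2 and populations N from Table 1. The confidence level is 95% (z = 1.96). The protocol does not state the proportion p or whether a finite population correction was used. I assume p = 0.5 with the correction, and test that assumption on the entries that are not in dispute.

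**Formula.** Margin = 1.96 × sqrt(p(1 − p)/n) × sqrt((N − n)/(N − 1)).

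**Step 1: reproduce the plan's other figures (percent).**

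| Group | n | N | Computed | Stated |
|---|---|---|---|---|
| All | 2400 | 4002 | 1.27 | 1.27 |
| Specialists | 595 | 992 | 2.54 | 2.55 |
| Western | 350 | 583 | 3.31 | 3.33 |
| Midwest | 289 | 481 | 3.65 | 3.65 |
| Southwest | 469 | 783 | 2.87 | 2.87 |
| South Central | 446 | 744 | 2.94 | 2.94 |
| South Atlantic | 346 | 577 | 3.34 | 3.34 |
| North East | 500 | 834 | 2.78 | 2.78 |
| Endodontists | 80 | 133 | 6.94 | 7.00 |
| Pediatric dentists | 102 | 170 | 6.16 | 6.20 |
| Periodontists | 92 | 154 | 6.50 | 6.59 |
| Prosthodontists | 49 | 81 | 8.85 | 9.00 |
| Oral/maxillofacial surgeons | 41 | 68 | 9.72 | 10.00 |
| Orthodontists | 231 | 386 | 4.09 | 4.10 |

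The largest gap is 0.28 points. Western gives 3.33 with n = 349, the sum of its own two cells (249 + 100). The six stated regional values have mean 3.15 and SD 0.34, as the text says. Without the correction nothing matches: all respondents would be 2.00 and specialists 4.02.

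**Step 2: general dentists.**

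- 1.96 × sqrt(0.25/1805) = 2.31%.
- Correction: sqrt((3010 − 1805)/3009) = sqrt(1205/3009) = 0.633.
- Margin: 2.31% × 0.633 = **1.46%**, against 0.05% stated. For this one cell the ratio is 1.46/0.05 = 29.

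**Step 3: a check that needs only the table.** The sampling fractions are 1805/3010 = 0.60 and 2400/4002 = 0.60. At equal fractions and the same p, margins scale with 1/sqrt(n), so the 1,805 should have about 1.27 × sqrt(2400/1805) = 1.27 × 1.153 = 1.46. A value below 1.27 is not possible on the table's terms.

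**Step 4: can another reading give 0.05%?**

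- N = 3002 instead of 3010: 1.46%.
- p = 0.1: 0.88%; p = 0.01: 0.29%.
- 80% instead of 95% confidence: 0.95%.
- Keeping p = 0.5, about 3,008 of the 3,010 general dentists would have to respond.
- Keeping n = 1,805, the true proportion would have to be near 0.03%, about half a respondent.
- Reading 0.05 as a proportion (5%) fails as well: the text prints a percent sign, the other entries are percentages, and 5% is not 1.46%.

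**Step 5: the general-dentist count.** The regional counts in Table 1 sum to 415 + 350 + 594 + 606 + 446 + 599 = 3010, and 3010 + 992 = 4002. The text's 3002 gives 3002 + 992 = 3994, which is not the total it states.

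**Step 6: effect on the generalist-specialist comparison** (independent groups, p = 0.5 in both).

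- From the printed margins: sqrt(0.05² + 2.55²) = 2.55 points.
- From the recomputed margins: sqrt(1.46² + 2.54²) = 2.93 points.

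**The case against.** The strongest reply is that nothing in the study depends on this number. Section 11.2 calls the objectives descriptive or exploratory, and the expected n is the available network times a 60% response rate. No quota, stopping rule or analysis uses a planning margin. At 1.46%, general dentists still have the smallest margin of any single category, so the sample is no less adequate than before. All of this stands, and it limits the weight of the point.

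It can also be said that the formula is inferred and that the match is approximate for the small specialties (9.72 against 10.00 at worst). That is true, and p = 0.5 with the correction should be read as an assumption. Gaps of that size do not explain 1.46 against 0.05, and the comparison with the 1.27% for all respondents needs only that the table uses one p throughout.

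A reader might infer more than the document supports, in three ways:

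- **That the margins are the sole basis for the sample size.** They are not. Section 11.2 also rests it on the number of dentists available and on a cited questionnaire-design guideline for effect sizes.
- **That one-point differences among general dentists would be taken as real.** Nothing in the protocol uses a planning margin to judge observed differences, and a margin for a single proportion is not a criterion for a difference.
- **That the 29-fold ratio describes the study's precision.** It describes one cell. Specialists dominate the margin of the comparison, which moves by about 0.4 points.

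**Conclusion.** The stated 0.05% is wrong in both the text of section 11.2 and Table 2. The value consistent with the rest of the table is 1.46% (n = 1,805, N = 3,010, 95% confidence). This rests on p = 0.5 and a finite population correction, neither of which the protocol states; both are supported by the 14 other entries. That 0.05% cannot be right follows from the table alone.

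The error overstates the precision for three quarters of the expected sample. The implied margin for a generalist-specialist difference is 2.93 points, not about 2.55. Sample size, recruitment and analyses are unaffected, so this is a wrong precision figure to correct and not a flaw in the design. The 3002 in the text is a separate clerical slip that leaves the 1.46% unchanged.

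**What to change.** - Replace 0.05% by 1.46% for general dentists in the text of section 11.2, and 0.05 by 1.46 in the category margin row of Table 2.
- Replace 3002 by 3010 general dentists in the text, in line with Table 1 and the total of 4002.
- Preferably add one sentence stating that the margins assume a proportion of 0.5 and a finite population correction, so that the table can be checked.

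The uncorrected 2.31% should not be put into this cell alone, because it would then disagree with every other entry. It is an option only if all margins are recomputed without the correction.

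The cost is two replaced figures in the text and one in the table. The stated precision for general dentists becomes less favourable, and nothing else in the plan changes.
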